6.1 Subject Inclusion Criteria

- Newly diagnosed patients with histologically confirmed MM based on the following criteria:
 - Clonal plasma cells in the bone marrow
 - Measurable disease within the past 4 weeks defined by any one of the following:
 - Serum monoclonal protein ≥ 1.0 g/dL
 - Urine monoclonal protein >200 mg/24 hour
 - Involved serum immunoglobulin free light chain > 10 mg/dL AND abnormal kappa/lambda ratio
- Evidence of underlying end organ damage and/or myeloma defining event attributed to underlying plasma cell proliferative disorder meeting at least one of the following:
 - Hypercalcemia: serum calcium >0.25 mmol/L (> 1 mg/dL) above upper limit of normal or ≥ 2.75 mmol/L (11 mg/dL)
 - Anemia: hemoglobin value <10 g/dL or > 2 g/dL below lower limit of normal
 - Bone disease: ≥ 1 lytic lesions on skeletal X-ray, CT, or PET-CT. For patients with 1 lytic lesion, bone marrow should demonstrate $\geq 10\%$ clonal plasma cells
 - Clonal bone marrow plasma cell percentage $\geq 60\%$
 - Involved/un-involved serum free light chain ratio ≥ 100 and involved free light chain >100 mg/L.
 - > 1 focal lesion on magnetic resonance imaging study (lesion must be >5 mm) in size
- Creatinine Clearance ≥ 60 ml/min. CrCl can be measured or estimated using Cockcroft-Gault method, MDRD, or CKD-EPI formulae
- Age ≥ 18 years at the time of signing the informed consent documentation
- Eastern Cooperative Oncology Group (ECOG) performance status 0-2
- Absolute neutrophil count (ANC) ≥ 1.0 K/uL, hemoglobin ≥ 8 g/dL, and platelet count ≥ 75 K/uL, unless if cytopenias are deemed to be due disease at discretion of clinical investigator. Transfusions and growth factors are permissible.
- Adequate hepatic function, with bilirubin < 1.5 x the ULN, and AST and ALT < 3.0 x ULN.

- All study participants must be able to tolerate one of the following thromboprophylactic strategies: aspirin, low molecular weight heparin or warfarin (coumadin) or alternative anti-coagulant.
- All study participants must be registered into the mandatory eREMS® program, and be willing and able to comply with the requirements of REMS®.

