- After receiving 4 or more cycles, patients who are considered to be eligible for subsequent high dose therapy/autologous stem cell transplant (ASCT) will be recommended to undergo autologous stem cell harvesting for potential use in the future. For patients who choose to undergo stem cell harvest, the subsequent cycle may be delayed for up to 7 weeks.

Cohorts 1, and 2

- Patients achieving ≥PR at end of 4 cycles will continue to receive the planned total of 8 cycles of combination therapy.
- Patients <PR after completing 4 cycles will go off study therapy.
- After completion of protocol therapy, patients will remain on study for an additional 3 years for survival analysis, including annual MRD assessment when appropriate.

Daratumumab was FDA approved for the indication of relapsed myeloma in November 2015. The initial approval was single drug used for 3rd line therapy. In October of 2016 FDA label was updated to include daratumumab with Revlimid/dexamethasone as 2nd line therapy; also the updated FDA label include daratumumab with Velcade/dexamethasone as 2nd line therapy. In June 2017, the FDA label was updated again; daratumumab with Pomalidomide/dexamethasone as 2nd line therapy. There is an ongoing randomized phase 3 study investigating daratumumab with Revlimid/dexamethasone as front line therapy. The drug combination we are testing (carfilzomib, daratumumab with Revlimid/dexamethasone) has been assessed in a phase 1 study which was recently presented at ASCO in June 2017.²⁵ In the phase 1 trial the dosing of carfilzomib was 70 mg/m² once a week; we are planning on giving 36 mg/m² twice a week in cohort 1 since that is the NCCN approved dose and 56mg/m² once a week in cohort 2.

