12.0 CRITERIA FOR THERAPEUTIC RESPONSE/OUTCOME ASSESSMENT

Disease Parameters

- a) A "measurable" serum M-protein is ≥ 1 g/dL or a "measurable" urine M-spike is ≥ 200 mg/24 hours or "measurable light chains" are either a serum kappa or lambda FREE light chain of ≥ 10 mg/dL along with an abnormal kappa to lambda free light chain ratio, patient is considered to have "measurable" disease.
- b) The serum free light chain (FLC) assay is of particular use in monitoring response to therapy in patients who have light-chain disease. When using this assay, it is important to note that

the FLC levels vary considerably with changes in renal function and do not solely represent monoclonal elevations. Thus both the level of the involved and the uninvolved FLC isotype (i.e., the involved/uninvolved ratio or involved-uninvolved difference) should be considered in assessing response. The serum FLC assay should be used in assessing response if the baseline level of the involved FLC is ≥ 10 mg/dL and abnormal kappa/lambda ratio (when primary determinant of response).

- c) For patients with initial baseline 24-hr UPEP samples demonstrating ≥ 100 mg/24 hrs, patients will continue to have 24-hr UPEP samples day 1 of each cycle. Once 24-hr UPEP is < 100 mg/24 hrs, patient can have random UPEP with IFE until achieving negativity. If initial baseline 24-hr UPEP sample is IFE positive and/or < 100 mg/24, patients can have random UPEP samples with IFE until achieving negativity. Once random UPEP and IFE is negative, no further urine samples are needed (unless primary determinant of response)
- d) In order to be classified as a response, confirmation of serum monoclonal protein, serum immunoglobulin free light chain (when primary determinant of response) and urine monoclonal protein (when primary determinant of response) results must be made by verification on two consecutive determinations at different timepoints.
- e) Compression fracture does not exclude continued response and may not indicate progression; findings of worsening compression fracture will be subject to interpretation of the clinical investigator.

Minimal Residual Disease

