 - Serum and urine M-protein detectable by immunofixation but not on electrophoresis or 90% or greater reduction in serum M-protein plus urine M- protein level <100 mg per 24h. If the serum and urine M-protein are unmeasurable, a $\geq 90\%$ decrease in the difference between involved and uninvolved FLC levels is required in place of the M-protein criteria.
- d) Partial Response (PR)
 - $\geq 50\%$ reduction in M protein and reduction in 24-h urinary M-protein by $\geq 90\%$ or to < 200 mg per 24h . If the serum and urine M-protein are unmeasurable, a $\geq 90\%$ difference between involved and uninvolved FLC levels is required in place of the M-protein criteria
- e) Stable Disease (SD)
 - Not meeting criteria for CR, VGPR, PR or progressive disease. All categories also require no known evidence of progressive or new bone lesions if radiographic studies were performed. Radiographic studies are not required to satisfy these response requirements.
- f) Progressive disease (PD)
 - Requires any one or more of the following:
 - Increase of $\geq 25\%$ of nadir in:
 - Serum M-component and/or (absolute increase must be ≥ 0.5 g/dl. The serum M-component increases of ≥ 1 gm/dl are sufficient to define relapse if starting M-component is ≥ 5 gm/dl.
 - Urine M-component and/or (the absolute increase must be ≥ 200 mg/24h
 - Only in patients without measureable serum and urine M-protein levels: the difference between involved and uninvolved FLC levels. The absolute increase must be >10 mg/dl.
 - Bone marrow plasma cell percentage: the absolute % must be $\geq 10\%$
 - Definite development of new bone lesions or soft tissue plasmacytomas or definite increase in size of existing bone lesions or soft tissue plasmacytomas
 - Development of that can be attributed solely to the plasma cell proliferative disorder

g) Relapse from CR

- Any one or more of the following:
 - Reappearance of serum or urine M-protein by immunofixation or electrophoresis. (Appearance of monoclonal or oligoclonal bands that are different from original isotype may not be defined as “relapse from CR”. Often times, such bands may indicate fluctuations in immunological parameters that are not reflective of MM disease. In these situations, immunofixation and electrophoresis will be interpreted by the clinician before being labeled as “relapse”^{27,28}.
 - Development of $\geq 5\%$ light-chain restricted plasma cells in the bone marrow

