13.0 CRITERIA FOR REMOVAL FROM STUDY

Off-therapy Criteria

If a patient is removed off-study during cycles 1-4, the patient is considered not evaluable, which will allow another patient to replace this slot.

- Patients with medically concerning grade 3 or 4 adverse events related to drug therapy may be taken off therapy at the discretion of the principal investigator.
- Patients who require more than 2 dose reductions of Carfilzomib.
- Hematologic toxicity has not completely resolved or resolved to < grade 1 or baseline after 2 weeks of withholding treatment
- Therapy has been held for more than 3 weeks due to treating a grade 3 infection
- Grade 4 non-blistering rash or blistering rash of any grade
- Grade 4 neuropathy
- Grade 4 hypersensitivity reaction
- Patient experiencing significant cardiac event as outlined in section 9.5
- Patient completes the protocol treatment
- Progression of disease
- Patient chooses to go off therapy
- The principal investigator may remove patient from protocol therapy if deemed necessary due to medical conditions, compliance, etc.
- Patient becomes pregnant.
- Patient has < PR after 4 cycles

Off-Study Criteria

- Patient requests to be withdrawn from study
- Death
- Physician's determination that withdrawal is in the patient's best interest.
Patient has completed 1- and 3-year evaluation from end of therapy

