The study includes safety suspension rules; throughout the study we will monitor for grade 3 or higher heart failure. These safety suspension rules will be applied separately in the two cohorts. In the event that the rule is crossed (see Table below), the study will be suspended for that cohort and all safety data will be reviewed by the PI. We will report all SAEs per standard guidelines (Section 17.2). In addition, throughout the study we will monitor for grade 4 or higher adverse events related to study drugs; if the PI notices there is a safety signal, the study will be suspended and all safety data will be reviewed by the PI.

Failure Type	# of failures needed to suspend the study	Failure rate in the population	Probability boundary is crossed
Heart failure/Ischemic heart disease (grade 3 or higher) Or grade 4 or higher adverse events due to study drug.	3 in the first 17 patients 4 in the first 29 patients 5 patients at any point	0.05	0.1
		0.2	0.95

The above numbers apply for each of the cohorts. Each cohort will be assessed independently.

Secondary Objective. Objectives 1, 2, and 3 below will be evaluated separately for the two cohorts.

1. To evaluate the safety and tolerability of the combination therapy. Toxicities will be summarized by grade and cycle of therapy. Patients who receive any study drug will be included in this assessment.
2. To evaluate the rates of best overall response (partial response (PR) or better), very good partial response (VGPR) or better, and complete response (CR) or stringent CR (sCR) for the evaluable patients. See section 12.0 for response definitions. Response proportions along with exact 95% confidence intervals will be reported.
3. Kaplan-Meier methods will be used to estimate overall and progression-free survival. . Patients who receive any study drug will be included in this assessment.
4. To compare MRD techniques of multi-parametric flow cytometry with 1) next-generation sequencing and 2) mass spectrometry using summary statistics. Rates of concordance for the measures will be estimated. This will be evaluated among all MRD assessments.

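### For patients followed by free light chains alone, partial response has the same 90% cut-off as very good partial response, so the printed rule gives no usable PR grade at the mandatory cycle-4 stop

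*Combined protocol and SAP*

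**What the plan says.** Section 12.0 gives separate FLC rules for patients whose serum and urine M-protein are both unmeasurable:

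- VGPR, item c): "a $\geq 90\%$ decrease in the difference between involved and uninvolved FLC levels is required in place of the M-protein criteria".
- PR, item d): "a $\geq 90\%$ difference between involved and uninvolved FLC levels is required in place of the M-protein criteria".
- Progression, item f), lists among the quantities that must rise by at least 25% from nadir: "Only in patients without measureable serum and urine M-protein levels: the difference between involved and uninvolved FLC levels".

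For patients with measurable M-protein, the same items keep the grades apart: a serum reduction of at least 50% for PR and at least 90% for VGPR, each with a urine condition. Stable disease is the residual grade.

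FLC-only patients can enter the trial. Section 6.1 accepts any one of three forms of measurable disease, and the third is "Involved serum immunoglobulin free light chain > 10 mg/dL AND abnormal kappa/lambda ratio". Section 12.0, Disease Parameters b), makes FLC a response measure for such patients: "The serum FLC assay should be used in assessing response if the baseline level of the involved FLC is ≥ 10 mg/dL", with an abnormal ratio. It gives no percentage for PR.

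The grade decides treatment. Section 9.0 states: "Patients <PR after completing 4 cycles will go off study therapy". Section 13.0 repeats it as an off-therapy criterion: "Patient has < PR after 4 cycles". Section 14.0 counts these patients as MRD positive in the primary analysis. The same grade feeds secondary objective 2: "To evaluate the rates of best overall response (partial response (PR) or better), very good partial response (VGPR) or better".

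**The concern.** The PR line carries the VGPR percentage and omits the word that makes the VGPR line a measure of change. The VGPR and progression lines on either side both measure change in the FLC difference, so a decrease was probably intended. On that reading every patient who meets PR also meets VGPR. No FLC-only patient can be graded PR, and a fall of 50-89% becomes stable disease.

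Read literally, the clause compares two FLC levels at one visit, with no baseline and no stated denominator. It can then err in either direction. Neither reading gives a valid PR rule, and no other section supplies a cut-off.

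What is at stake is mainly the treatment of individual patients. A partial responder graded below PR is taken off therapy after cycle 4 and is counted as a non-responder in the PR-or-better rate. A patient followed by serum M-protein with the same proportional fall, who also meets the urine condition, continues. The effect on the primary endpoint is indirect. Section 12.0 already treats anyone below VGPR as MRD positive, so the only loss is the chance of converting during cycles 5-8.

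**Working it through.** **Grades, if a decrease was meant.** Let d be the percentage fall from baseline in involved minus uninvolved FLC.

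| d | As printed, 90% for both grades | With a 50% PR cut-off |
|---|---|---|
| below 50% | below PR, stop | below PR, stop |
| 50% to below 90% | below PR, stop | PR, continue |
| 90% or more | VGPR | VGPR |

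Illustration with assumed levels in mg/L: baseline 1000/10 gives a difference of 990. Cycle 4 at 300/10 gives 290. The fall is (990 − 290)/990 = 71%. As printed this is stable disease and the patient stops.

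**Grades, read literally.** Assume the denominator is involved FLC. Then 1 − 1/ratio ≥ 0.90 means a ratio of 10 or more, which a patient can meet before any treatment. With uninvolved FLC as the denominator, the cut-off is a ratio of 1.9. The rule can also fail a true responder: 120/10 falling to 50/10 takes the difference from 110 to 40, a 64% fall, but 40/50 = 80%, so the clause is not met. No patient count is possible here, because the baseline ratios are not given.

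**The plan's own design figures (Section 14.0).** Inputs: 28 patients in stage 1, continue with at least 12 MRD negative; 41 in total, success with at least 21; rates 0.40 and 0.60; type I and type II error 0.10 each.

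P(success) = Σ over x = 12 to 28 of b(28, x, p) × P(Bin(13, p) ≥ 21 − x).

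This gives 0.095 at p = 0.40 and 0.901 at p = 0.60, in line with the stated error rates. The design itself is not in question.

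**One misgraded patient, no assumption about frequency.** 1/41 = 2.4 points. For example, 41/41 = 100% (exact 95% CI 91.4-100) becomes 40/41 = 97.6% (87.1-99.9).

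**Expected effect per cohort.** The documents give none of the three inputs, so all are assumptions: f, the FLC-only share; q, the share of those with a 50-89% fall at cycle 4; c, the share of those who would have become MRD negative in cycles 5-8. Staff are assumed always to apply the printed line as a 90% decrease.

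- Patients stopped = 41 × f × q
- Points lost from PR-or-better = 100 × f × q
- MRD-negative results lost = 41 × f × q × c
- Effective MRD-negative rate = 0.60 − f × q × c

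| f, q, c | Stopped | Points lost | MRD negatives lost | Rate | Power |
|---|---|---|---|---|---|
| 10%, 5%, 25% | 0.205 | 0.5 | 0.05 | 0.59875 | 0.898 |
| 15%, 10%, 40% | 0.615 | 1.5 | 0.25 | 0.594 | 0.886 |
| 20%, 15%, 60% | 1.23 | 3.0 | 0.74 | 0.582 | 0.853 |

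If staff apply the printed line half the time, the lowest and highest cases give power 0.899 and 0.879. If they never apply it, power stays at 0.901.

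**Wider inputs.** With f = 5-20%, q = 10-50% and c = 60%, the number stopped is 0.2-4.1 (41 × 0.20 × 0.50 = 4.1 at the top). Power is 0.894 at the low end and 0.693 at the high end.

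**The case against.** The strongest reply is that the protocol names an outside standard. Section 1.0 says response is assessed by the uniform myeloma criteria, and Section 12.0 heads its list as the IMWG criteria. Staff who know those criteria may apply them and never meet the faulty line, and the loss is then zero. This is a fair limit on the size of the problem. It does not remove it: Section 12.0 presents the printed list as those criteria, the objectives send the reader to Section 12.0 for definitions, and nothing says the source overrides the text.

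Second, the empty PR grade appears only if a decrease is read into the clause, and the missing words could have been lost when the PDF was read. That is possible, but it would not explain a PR percentage equal to the VGPR percentage. The literal reading does not work either.

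Third, the expected counts rest wholly on assumed inputs, and reasonable choices differ more than threefold at the upper end (1.2 against 4.1 patients). This stands. The power figures show a range and are not estimates. Only the 2.4 points per misgraded patient is free of assumed frequencies.

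Fourth, the background suggests few patients near the boundary. Section 3.0 reports a 98% overall response rate in the earlier three-drug study and, as of May 2019, 100% MRD negativity as best response in Cohort 2. The first is neither a cycle-4 nor an FLC-only figure, and the second had 18 patients still pending. Both point towards a small effect without settling it.

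**Conclusion.** The concern holds. As printed, Section 12.0 d) gives no valid PR grade for FLC-only patients, who are eligible and subject to a mandatory stop when graded below PR after cycle 4. Confidence is high for the duplicated 90% and the lack of any other cut-off. It is lower for the consequences, which depend on how many such patients enrol and on which text staff apply.

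The severity is minor. On the narrower assumptions about one patient per cohort or fewer is affected, the PR-or-better rate loses up to 3.0 points, and power stays at 0.853 or above; wider inputs would cost more. The documents do not show that anyone has been misgraded.

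**What to change.** In Section 12.0 d), restate the FLC clause as a decrease from baseline of at least 50% in involved minus uninvolved FLC. The 50% mirrors the protocol's own serum M-protein rule for PR and lies below the VGPR value; verify it against the cited IMWG criteria before adopting it. Then re-check the cycle-4 and best-response grades of any FLC-only patients already enrolled.

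The cost is one line of text and a review of a few records. Sample size, visits and decision rules do not change.

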13.0 CRITERIA FOR REMOVAL FROM STUDY

Off-therapy Criteria

If a patient is removed off-study during cycles 1-4, the patient is considered not evaluable, which will allow another patient to replace this slot.

- Patients with medically concerning grade 3 or 4 adverse events related to drug therapy may be taken off therapy at the discretion of the principal investigator.
- Patients who require more than 2 dose reductions of Carfilzomib.
- Hematologic toxicity has not completely resolved or resolved to < grade 1 or baseline after 2 weeks of withholding treatment
- Therapy has been held for more than 3 weeks due to treating a grade 3 infection
- Grade 4 non-blistering rash or blistering rash of any grade
- Grade 4 neuropathy
- Grade 4 hypersensitivity reaction
- Patient experiencing significant cardiac event as outlined in section 9.5
- Patient completes the protocol treatment
- Progression of disease
- Patient chooses to go off therapy
- The principal investigator may remove patient from protocol therapy if deemed necessary due to medical conditions, compliance, etc.
- Patient becomes pregnant.
- Patient has < PR after 4 cycles

Off-Study Criteria

- Patient requests to be withdrawn from study
- Death
- Physician's determination that withdrawal is in the patient's best interest.
Patient has completed 1- and 3-year evaluation from end of therapy

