4.0 OVERVIEW OF STUDY DESIGN/INTERVENTION

4.1 Design

Patients with newly diagnosed MM will be enrolled on the Phase II study and treated with 4-drug combination of daratumumab, carfilzomib, lenalidomide, and dexamethasone. New data demonstrates that 56mg/m² has the same safety profile as 36mg/m² in the newly diagnosed multiple myeloma patients treated with the 3-drug combo KRd²⁶. Efficacy for Carfilzomib has a dose-response association and emerging data indicates that once a week 56mg/m² and twice a week 36mg/m² translates into similar CR rates. To make the 4 drug combinations more convenient to patients, the study has expanded to include two parallel cohorts; one cohort with twice a week 36mg/m² and the other cohort with once a week 56mg/m² Carfilzomib, respectively. Up to 82 patients will be enrolled on study; 41 patients per cohort. Clinical response as well as MRD rates will be determined the same way in both cohorts. The overall goal is to develop a highly efficacious combination, and to optimize the dosing so it becomes as convenient as possible. The combination of efficacy and convenience is of direct benefit to patients.

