Allergic Reaction/Hypersensitivity	
 Grade 2: Hold carfilzomib until \leq Grade 1 and resume at full carfilzomib dose
Tumor Lysis Syndrome (≥ 3 of the following: $\geq 50\%$ increase in creatinine, uric acid, or phosphate; $\geq 30\%$ increase in potassium; $\geq 20\%$ decrease in calcium; or 2-fold increase in LDH)	Hold carfilzomib until all abnormalities in serum chemistries have resolved. Resume at full dose
Herpes zoster or simplex of any grade	Hold carfilzomib until lesions are dry. Resume at full dose
Neuropathy	Grade 2 treatment emergent neuropathy with pain: Hold carfilzomib until resolved to \leq Gr 1 without pain. Then restart at next dose level reduction.
Congestive Heart Failure	Patients with clinical symptoms and/or significant changes in EF ($>10\%$) will hold carfilzomib and repeat cardioechogram as clinically appropriate; if persisting/worsening clinical symptoms and/or significant changes in EF that is attributed to the therapy, the patient will be taken off the trial.
Hypertension (uncontrollable by medications, hypertension emergencies, or >3 episodes of hypertension urgencies)	
Hypertension uncontrollable by medications or >3 episodes of hypertension urgencies – hold carfilzomib and decrease to next dose level.
 
Hypertension emergency – stop therapy and go off protocol

Myocardial infarction	Any patient experiencing myocardial infarction will stop therapy and go off protocol
Posterior reversible encephalopathy syndrome (PRES)	If PRES is suspected, hold carfilzomib. Consider evaluation with neuroradiological imaging, specifically MRI, for onset of visual or neurological symptoms suggestive of PRES. If PRES is confirmed, permanently discontinue carfilzomib. If the diagnosis of PRES is excluded, carfilzomib administration may resume at the same dose, if clinically appropriate.

Carfilzomib Toxicities	Specific Dosing Modifications
Thrombotic microangiopathy (TMA)	If the diagnosis is suspected, hold carfilzomib and manage per standard of care including plasma exchange as clinically appropriate. If TMA is confirmed, permanently discontinue carfilzomib. If the diagnosis is excluded, carfilzomib can be restarted.

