9.4 Monitoring

- 9.4.1 Routine labs (CBC, chemistry panel 14, LDH, magnesium, uric acid, phosphate) will be performed at baseline and on Day 1, 2, 8, 15, and 22 of cycle 1 and Day 1 of each cycle thereafter, end of therapy, and 1-year and 3-year after end of therapy. Myeloma tests include serum protein electrophoresis, serum immunofixation, beta-2 microglobulin, quantitative immunoglobulins and serum free light chains assay will be performed at baseline and Day 1 of each cycle, end of therapy, and 1-year and 3-year after end of therapy. Serum Lymphocyte subsets will be performed at baseline, Day 1 of cycle 4, and end of treatment. Routine labs, myeloma labs, and lymphocyte subsets can be performed 24 hrs in advance.
- 9.4.2 For patients with initial baseline 24-hr UPEP samples demonstrating ≥ 100 mg/24 hrs, patients will continue to have 24-hr UPEP samples day 1 of each cycle. Once 24-hr UPEP is < 100 mg/24 hrs, patient can have random UPEP with IFE until achieving negativity. If initial baseline 24-hr UPEP sample is IFE positive and/or < 100 mg/24, patients can have random UPEP samples with IFE until achieving negativity. Once random UPEP and IFE is negative, no further urine samples are needed (unless patient's disease is primarily measurable by 24 hr urines i.e. oligosecretory/hyposecretory)
- 9.4.3 Patients will have clinic visits with H&P or standard progress notes assessing for toxicity/side effects on Day 1, 8, and 15, of cycle 1 and Day 1 of each cycle thereafter 1-month after end of therapy, 1-year after end of therapy and 3-year after end of therapy. Treatment window for day 1 of start of each cycle is ± 7 days. Treatment window for intra-cycle carfilzomib doses is ± 2 days. Vital signs will be checked prior to administration of study drugs carfilzomib or daratumumab in all cycles.

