14.0 BIOSTATISTICS

Primary Objective:

This is a phase II study to assess the efficacy of up to 8 cycles of combinational therapy with daratumumab, carfilzomib, lenalidomide, and dexamethasone in newly diagnosed multiple myeloma (MM) patients. The primary objective of the study is to assess the rate of MRD negativity at the end of planned treatment up to 8 cycles for the combination therapy using multiparametric flow cytometry. Patients with < PR after completing 4 cycles will be included in the analysis of the primary objective and will be considered MRD positive. Patients who receive any study drug and have at least one post-baseline disease assessment will be considered evaluable for the primary endpoint. The rate of MRD negativity will be assessed for each cohort, separately.

This study is designed to distinguish between an unpromising MRD rate of 40% and a promising rate of 60%¹. The unpromising rate of 40% is based on the 1st generation sequencing-based MRD rate in the referenced Korde et al study. The flow cytometry-based MRD assessment that will be used as part of this study has been shown to have similar performance as the sequencing-based MRD assessment used in that study.

The study includes two cohorts, which of each will receive up to 8 cycles of combination therapy. The two cohorts are defined based on the schedule and dosing of carfilzomib. These cohorts are described in Section 4.0. The following Simon two-stage design will be evaluated separately for the two cohorts.

Using a Simon's minimax two-stage design, the first stage of the study will enroll 28 patients. If at least 12 have a best response of MRD negativity within 8 cycles of therapy, the study will continue to enroll remaining patients up to a total of 41 patients. If, after 28 patients have accrued, it is uncertain whether the response threshold will be met, accrual will be held until the determination can be made. If 21 of the 41 patients have a best response of MRD negativity within 8 cycles of therapy the study will be considered to be successful. The study is designed to have a type I error and a type II error of 0.10. The maximum sample size is 41 patients.

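### Section 13's rule that early off-study removals are not evaluable and replaceable conflicts with Section 14's evaluability rule and the cap of 41 per cohort; applied as written, it could inflate the primary MRD-negativity rate

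*Combined protocol and SAP*

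**What the plan says.** Section 13.0, under the Off-therapy Criteria heading and ahead of its list: "If a patient is removed off-study during cycles 1-4, the patient is considered not evaluable, which will allow another patient to replace this slot". The list beneath it includes "Progression of disease" and "Patient has < PR after 4 cycles", along with related grade 3 or 4 events, cardiac events and patient choice. A separate Off-Study list in the same section names a request to withdraw, death, physician's determination and completed follow-up.

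Section 14.0, on the primary objective: "Patients who receive any study drug and have at least one post-baseline disease assessment will be considered evaluable for the primary endpoint". It adds: "Patients with < PR after completing 4 cycles will be included in the analysis of the primary objective and will be considered MRD positive". Section 14 sets the two-stage rule for each cohort (at least 12 of 28 to continue, 21 of 41 for success) and a maximum of 41 patients. It reports response rates for evaluable patients, and safety, PFS and OS for everyone who receives any study drug.

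Section 4.1 gives the overall cap: "Up to 82 patients will be enrolled on study; 41 patients per cohort". Neither Section 4.1 nor Section 14 mentions replacement.

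Section 9.4 fixes when disease is first reassessed. Of the myeloma tests it says: "quantitative immunoglobulins and serum free light chains assay will be performed at baseline and Day 1 of each cycle, end of therapy".

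**The concern.** Two current sections define evaluability differently. Take a patient who has the cycle 2 day 1 myeloma tests and dies in cycle 3. Under Section 14 this patient is in the primary denominator and, without an MRD-negative result, counts against the regimen. Under Section 13 the same patient is not evaluable and another patient takes the slot.

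At stake are the primary MRD-negativity rate, the stage 1 decision, the final decision in each cohort, and the response rates, which also rest on evaluable patients. Removal in the first four cycles is unlikely to be independent of outcome: progression, early death and serious toxicity should include more non-responders than the cohort as a whole. Replacing such patients would move the analysed rate upward while the thresholds stay fixed. It would also take the number treated above 41 in a cohort, or else leave fewer than 41 counted.

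**Working it through.** **1. Who falls under each rule.**

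| Patient, dosed, with cycle 2 day 1 tests done | Section 14 | Section 13, narrow reading (Off-Study list only) | Section 13, broad reading (Off-therapy list too) |
|---|---|---|---|
| Dies or withdraws from the study in cycles 2-4 | Evaluable | Not evaluable, replaced | Not evaluable, replaced |
| Stops for progression or toxicity in cycles 2-4 | Evaluable | Stays | Not evaluable, replaced |
| Below PR after completing 4 cycles | Evaluable, MRD-positive | Stays | Unclear whether this is during cycles 1-4 |

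The first row conflicts on both readings; the second conflicts on the broad reading only.

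**2. The plan's own design.** Inputs from Section 14: null rate 0.40, target rate 0.60, 28 patients at stage 1, 41 in total, cut-offs 12 and 21 (the latter read as at least 21), error limits 0.10.

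P(success | p) = sum over x from 12 to 28 of P(X1 = x | 28, p) × P(X2 ≥ 21 − x | 13, p)

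- At p = 0.40: 0.0951 (type I error).
- At p = 0.60: 0.9009 (power).
- Probability of stopping at stage 1 when p = 0.40: 0.551.

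A search finds no feasible design with a total below 41, and at 41 the stated cut-offs give the smallest expected size under the null (33.8). The sample size is correct for 41 patients counted without outcome-related exclusion.

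**3. Effect of applying Section 13.** Let d be the share of treated patients removed and replaced, and m the MRD-negative share among them. Neither is in the documents, so both are assumptions. With an all-treated rate of 0.40:

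rate among counted patients = (0.40 − d × m) / (1 − d)

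For example, d = 0.10 and m = 0 give 0.40 / 0.90 = 0.444; d = 0.10 and m = 0.20 give 0.38 / 0.90 = 0.422. Putting these rates into the formula in step 2:

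| d | Type I error, m = 0 | m = 0.20 | m = 0.40 | Expected treated for 41 counted, 41/(1 − d) |
|---|---|---|---|---|
| 0 | 0.095 | 0.095 | 0.095 | 41.0 |
| 2.5% | 0.120 | 0.107 | 0.095 | 42.1 |
| 5% | 0.151 | 0.121 | 0.095 | 43.2 |
| 10% | 0.234 | 0.155 | 0.095 | 45.6 |
| 15% | 0.349 | 0.199 | 0.095 | 48.2 |

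The m = 0 column is the upper end for each d.

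**4. In patient counts.** A cohort declared successful at 21/41 (51.2%) after four replaced non-responders has 21/45 (46.7%) MRD-negative among those treated.

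**The case against.** A reader might infer that anyone who stops in cycles 1-4 is dropped and that early failures are therefore already deleted from the primary denominator. The documents do not support that.

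- **Scope.** The sentence says off-study, and Section 13 lists off-study reasons separately from off-therapy reasons. Read literally, progression and toxicity do not trigger it. This stands as a limit on how many patients are affected. It does not remove the conflict, because death and withdrawal after a first assessment remain. The sentence's position under the off-therapy heading keeps the broad reading open, and loose wording elsewhere does not help: the Section 9.3 carfilzomib table says "Any patient experiencing myocardial infarction will stop therapy and go off protocol".
- **Which rule governs.** Section 14 is the only text that defines evaluability for the primary endpoint, and it expressly keeps patients below PR after four cycles. Section 13 mentions neither MRD nor the primary endpoint. Early failures are lost only if Section 13 is applied over Section 14. This stands: the defect is an unresolved conflict, not an established deletion.
- **Responders among those removed.** It is tempting to assume that early removals are almost never MRD-negative. Section 3 reports an average of 4.5 cycles to MRD negativity in Cohort 2 (5.36 in Cohort 1) and time to sCR from 2 cycles in the prior KRd study, so some patients may convert before removal. This stands, and it is why the m = 0 figures are upper ends.
- **Section 14's own gap.** Its rule leaves out dosed patients with no post-baseline assessment. With tests on day 1 of each cycle, these are mainly patients who leave within about the first 28 days. This is a smaller, separate matter.
- **Survival follow-up.** Section 14 includes all dosed patients in PFS and OS, and the Section 10 schedule notes collect these data on all patients. No separate request is needed.

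**Conclusion.** The conflict is real and affects the primary analysis. Sections 13 and 14 cannot both be followed for a patient who dies or withdraws after a first assessment but within the first four cycles, and replacement does not fit a cap of 41 per cohort. No text ranks the rules.

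The size depends on an early-removal rate that the documents do not give. If Section 13 is applied and removed patients are MRD-negative less often than the 40% null rate, type I error exceeds the planned 0.10 in every scenario computed: 0.107 to 0.120 at 2.5% removal, and 0.155 to 0.234 at 10%, for 20% down to none of the removed patients being MRD-negative. On the narrow reading a small removal rate is the more plausible. There is no inflation if removed patients respond at 40%, and none from this source if Section 14 is applied. The design itself (0.095 and 0.901) is sound. The point should be settled before the denominators are fixed, because the choice can change the stage 1 and final decisions.

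**What to change.** 1. In Section 13, delete the sentence on evaluability and replacement, or limit replacement to patients who never receive study drug.
2. In Section 14, state one denominator rule that applies at stage 1, at the final analysis and to the response rates. Preferably this is all patients who receive any study drug, the population already used for safety, PFS and OS. Anyone without a qualifying MRD-negative result counts as MRD-positive, which extends Section 12's existing treatment of undeterminable MRD status. An MRD-negative result reached before removal still counts.
3. At minimum, state that Section 14's evaluability rule governs, and that dosed patients are not replaced, so that the cap of 41 per cohort holds.

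The cost is about two sentences. The sample size and cut-offs do not change. The reported MRD-negativity and response rates may be slightly lower.
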